5.0 AGENT ADMINISTRATION

5.1 Dose Regimen and Dose Groups

Both Brevail® and matched placebo are to be provided by Lignan Research, Inc. to the investigational pharmacy at each participating institution.

Brevail® (containing 50 mg of the active ingredient SDG) or placebo (containing the same filler material but without SDG) will be given to all trial participants for the 12 months of participation. All subjects should have off-study procedures no later than within 36 hours of the last dose of SDG or placebo. However, if a participant stops study agent prematurely in an unscheduled situation, she should come in for biomarker re-assessment as early as possible.

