5.9 Dose Modification

Dose modifications will not be utilized for this study. Because study agent is only available in a single dose capsule, no dose modification option is available. If a subject is experiencing adverse events or is having a medical procedure that requires a brief suspension of SDG, this must be noted in the CRF on the dose suspension page. At the discretion of the PI, subjects may be removed from participation for significant dose suspension time periods.

Subjects with grade 2 adverse events considered to be related to study agent will have the agent suspended until the toxicity has resolved. The agent will then be resumed. If toxicity again occurs, and is thought to be agent-related, the agent will be permanently stopped. Grade 2 hot flashes or menstrual irregularities will not be cause for suspending study agent.

Subjects who experience grade 3-4 toxicity will have the study agent suspended. The agent may be re-instituted after resolution of the adverse event, providing the investigator feels relatively certain that the toxicity is not due to the study agent and that resuming agent will not affect recovery from the condition

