8.2.3 Severity of adverse events

Identify the adverse event using the NCI Common Terminology Criteria for Adverse Events (CTCAE) version 4.0. The CTCAE provides descriptive terminology and a grading scale for each adverse event listed. A copy of the CTCAE can be found at <http://ctep.cancer.gov>.

AEs will be assessed according to the CTCAE grade associated with the AE term. AEs that do not have a corresponding CTCAE term will be assessed according to their impact on the participant's ability to perform daily activities as follows:

GRADE	SEVERITY	DESCRIPTION
1	Mild	Barely noticeable, does not influence functioning Causing no limitations of usual activities
2	Moderate	Makes participant uncomfortable, influences functioning Causing some limitations of usual activities
3	Severe	Severe discomfort, treatment needed Severe and undesirable, causing inability to carry out usual activities
4	Life threatening	Immediate risk of death Life threatening or disabling
5	Fatal	Causes death of the participant

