10.2 Data and Safety Monitoring Plan

The Data Safety and Monitoring Committee (DSMC) of the University of Kansas Cancer Center will provide annual review of this trial

The DSMC monitors data management and subject safety. Subject accrual is reviewed annually by the Protocol Review and Monitoring Committee of the University of Kansas Cancer Center. The DSMC also provides advice on the overall conduct of the study. Meetings will be held on an annual basis. Interval conference calls may be conducted as required. The functions of the DSMC are primarily those of an overview nature in regard to both data and safety, as detailed below.

All data collected for this trial will ultimately reside in a central trial specific database. Data accuracy and completeness will be monitored via inspection of summary reports prepared for the DSMC by the biostatistician for this project.

The subject cohort consists of essentially healthy women who are defined as being at high risk for the development of breast cancer, but do not have any clinical evidence of or suspicion for an

existing malignancy. As such, side effects that might be due to the study intervention are expected to be minimal but should be easily identified and monitored.

In regard to adverse events (AEs) or serious adverse events (SAEs), it is not deemed necessary for the DSMC to address these for individual subjects. Rather, all grade 4 toxicities are reported as an SAE to the institutional review board immediately.

In addition to the functions performed by the DSMC, an External Advisory Board (EAB) will serve in a general advisory role in regards to assessing the progress that is being made on the study. Subject accrual rates, and specifically problems with accrual that might impact on the ability of the trial to be completed, can be addressed by the EAB. Likewise, the EAB may make suggestions on other aspects that would improve the quality of the trial. The EAB consists of two individuals with experience in clinical prevention trial: [name]., of Mayo Clinic, Rochester, MN; and [name], of Johns Hopkins University, Baltimore, MD.

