11.2 Statistical Analysis

All analyses will be intent-to-treat. All subjects randomized will be evaluable for safety and all subjects that have both a pre and post specimen are evaluable for efficacy. Primary analysis of efficacy will be performed on all evaluable subjects and secondary analysis will be done on those subjects who received at least 6 months of study medication and were confirmed as being in the follicular phase for both RPFNA procedures. From our experience we have very little missing data; however, if the missing data rate is above 5%, we will use multiple imputation to impute these values to perform the primary and secondary analyses.

The primary outcome will be change in Ki-67 (percent of cells expressing Ki-67) from baseline to 12 months. The two-sample t-test will be used to compare the change in Ki-67 between the SDG

and placebo groups. Any difference in baseline values of Ki-67 between the two groups would be due to chance, however, if there is a significant difference, then analysis of covariance adjusting for baseline values will be performed. Due to potential skewness in these variables we will assess whether or not the Central Limit Theorem may be assumed. Given the sample size the existence of an extremely high degree of skewness would require the use of the Wilcoxon Signed Rank test.

For the secondary endpoints, similar methods as above will be used to compare the treatment and control groups at two time points for all markers, i.e., serum hormones and clinical laboratory tests. We will also correlate change in the primary biomarker Ki-67 with change in other markers (e.g., bioavailable estradiol, cytokines, RTqPCR results) using Pearson's correlation coefficient. Again, if there exists a high degree of skewness in these variables, Spearman's correlation will be utilized.

Multiple regression analysis will also be used to investigate whether changes in Ki-67 are due to variables other than treatment effect (e.g., age, cytromorphology, Gail risk; as well as the predictive effect of other biomarkers on modulation of Ki-67). Best subsets and stepwise approaches will be employed while controlling for treatment group.

For comparison of moderate or worse toxicities we will consider grade 3 toxicity or premature trial discontinuation as the critical events. The prevalence of events in the SDG vs. the placebo arm will be examined by Fisher's exact test.

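### The toxicity comparison is labelled moderate or worse but counts grade 3 toxicity or trial discontinuation, so most grade 2 (moderate) events fall outside it

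*Combined protocol and SAP*

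**What the plan says.** Section 11.2 (Statistical Analysis) sets the rule: "For comparison of moderate or worse toxicities we will consider grade 3 toxicity or premature trial discontinuation as the critical events". The two arms are then compared by Fisher's exact test.

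Section 8.2.3 grades events by CTCAE 4.0 and adds a fallback: "AEs that do not have a corresponding CTCAE term will be assessed according to their impact". The table that follows gives grade 1 as Mild, 2 as Moderate, 3 as Severe, 4 as Life threatening and 5 as Fatal. Its description of grade 2 is "Makes participant uncomfortable, influences functioning Causing some limitations of usual activities".

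Section 5.9 suspends the agent for related grade 2 events and continues: "If toxicity again occurs, and is thought to be agent-related, the agent will be permanently stopped". It makes an exception: "Grade 2 hot flashes or menstrual irregularities will not be cause for suspending study agent". It takes the higher grades together: "Subjects who experience grade 3-4 toxicity will have the study agent suspended". Section 10.2 adds that "all grade 4 toxicities are reported as an SAE to the institutional review board immediately".

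Section 5.10 lists the reasons for discontinuation. They include adverse events and death, and also administrative problems and withdrawal of consent.

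**The concern.** The label and the counted event disagree. On the only scale in the documents that links words to grades, moderate begins at grade 2, and nothing in the documents calls grade 3 moderate. A result obtained under the written rule would be reported under a description that it does not match.

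This bears on a stated hypothesis. Section 1.0 expects a favorable tolerability and quality of life profile, and Sections 2.1 and 3.2 build the case for wide uptake on good tolerability without medical monitoring. A null result reported as no difference in moderate or worse toxicity could be cited for that case even though most women with moderate events had not been counted.

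**Working it through.** The plan states no power or sample size for this comparison, so the only figures to reproduce are those of the pilot grade table.

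**Is there another test of graded events?** In Section 11.2, the sentence applying similar methods to secondary endpoints concerns markers (serum hormones and clinical laboratory tests). The later paragraph on adverse events and quality of life concerns mastalgia, menstrual cycle, follicular reserve and quality of life; it gives no grade and names no test. The Fisher comparison is therefore the only named between-arm test of graded events.

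**Which events count, grade by grade?**
- *Grade 2 (Moderate).* Not in the toxicity limb. It enters only if the woman also discontinues the trial. Section 5.9 gives one route, permanent stopping after a recurrent related event, but exempts hot flashes and menstrual irregularities from suspension. Whether stopping the agent is the same as discontinuing the trial is not settled. Section 5.1 says that "if a participant stops study agent prematurely in an unscheduled situation, she should come in for biomarker re-assessment as early as possible", and Section 5.10 records discontinued treatment and discontinued observations together.
- *Grade 3 (Severe).* Counts.
- *Grade 4.* Read literally, not in the toxicity limb. Section 5.9 allows the agent to be resumed after a grade 3-4 event under stated conditions, so a woman with a grade 4 event can remain on trial and go uncounted.
- *Grade 5.* Counts through the second limb, because Section 5.10 lists death as a reason for discontinuation.

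**How far apart are the two thresholds in the pilot?** Inputs are the worst grade per woman from Section 2.4.4.5 and completion from Section 2.4.4.
- Table check: 7 + 17 + 23 + 2 + 0 = 49. Shares: 23/49 = 46.9% and 2/49 = 4.1%, matching the printed 47% and 4%.
- Worst grade 2 or higher: (23 + 2 + 0)/49 = 25/49 = 51.0%.
- Worst grade 3: 2/49 = 4.1%. No pilot woman had grade 4 or 5.

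**What could the discontinuation limb add?** Of 49 women, 45 completed and were evaluable, so at most 49 - 45 = 4 did not complete. One of these was the woman with grade 3 pelvic pain, who already counts. At most 3 others could have had a worst grade of 2, so the composite would have captured 2 + (0 to 3) = 2 to 5 of the 25 women and left out 20 to 23 (80% to 92%). If the woman with DCIS, the other grade 3 case, also did not complete, the range is 2 + (0 to 2) = 2 to 4 captured and 21 to 23 left out (84% to 92%). This carries the present rule over to a pilot whose own stopping rules are not given.

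**Do other measures fill the gap?** The BCPT checklist asks about the past four weeks (Appendix 1, item 8.1) and is completed at study entry and 12 months (Section 6.1). The breast pain questionnaire follows the same two visits and covers one symptom. The menstrual diary runs through the year (Sections 6.3.7 and 6.5.5) but records only bleeding and spotting. None compares graded events over the year.

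**The case against.** The best reply is that the rule itself is explicit. Section 11.2 says which events are critical and names the test. It may mean that, among moderate or worse toxicities, the critical ones are those that reach grade 3 or end participation. The Section 8.2.3 table formally covers only events without a CTCAE term, and Section 11.2 does not cite it. On this view a relabel is enough, and a grade 2 comparison is a preference. Part of this stands: the composite is a legitimate endpoint and should stay, and relabelling alone would remove the contradiction. But the announced question about moderate toxicity would then have no test, and the limited scope of the table supplies no other meaning for moderate.

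Stronger readings are tempting and should not be drawn:
- *That grades 4 and 5 are ignored.* A death enters through discontinuation, and a reference to worse events in the same sentence suggests no wish to drop severe ones. Only a grade 4 event in a woman who stays on trial is in doubt.
- *That toxicity is undefined as to cause.* Sections 5.9 and 10.2 use the word without regard to attribution; Section 5.9 treats relatedness as a separate judgement. The all-cause reading is the natural one.
- *That tolerability is otherwise unexamined.* The diary partly covers irregular menses, reported in 26% of pilot subjects and one of the two grade 2 categories exempt from suspension.
- *That 80% to 92% of moderate toxicity will be missed in this trial.* The pilot was single-arm and its rules are not given. The figure shows how common a worst grade of 2 was; it shows no bias or loss of power.

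**Conclusion.** The point holds as a mismatch between label and definition: the test called moderate or worse is in substance a severe-toxicity-or-discontinuation test. The pilot contrast, 51% against 4%, shows that the choice of threshold changes which women count and goes beyond wording. That contrast is illustrative and assumes that worst grade regardless of attribution is the relevant count. The primary Ki-67 analysis and its stated power are unaffected, and no figure in the plan is shown to be wrong. The change should be made because, as written, the test cannot support a statement about moderate toxicity.

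**What to change.** Before unblinding, reconcile Section 11.2 with Section 8.2.3:
1. Relabel the existing composite as grade 3 or higher toxicity or premature trial discontinuation, so that a grade 4 event in a woman who stays on trial is counted.
2. Add a Fisher's exact comparison of worst grade 2 or higher per woman, in all randomized women (the safety set of Section 11.2), regardless of attribution. If this is not added, draw no conclusion about moderate toxicity from the composite.

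Two clarifications are optional: state whether permanently stopping the agent counts as trial discontinuation in this analysis, and show the composite's components with discontinuation for adverse events separate from the other reasons in Section 5.10.

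The cost is wording and one added comparison. Severity grade (Section 8.2.2) and reason for discontinuation (Section 5.10) are already collected. The downside is one more safety comparison at an uncorrected 5% level, which Section 11.2 already accepts for secondary analyses, and background grade 2 events in both arms may dilute a true difference.

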1.0 OBJECTIVES

The overall objective is to determine whether the natural flaxseed lignan, secoisolariciresinol diglycoside (SDG), in amounts providing plasma lignan levels associated with reduced breast cancer risk, will favorably modulate risk biomarkers for breast cancer development. This will provide biologic evidence of SDG's potential for breast cancer chemoprevention. Based on a positive pilot study in which both Ki-67 and the proportion of women with atypical cytomorphology was reduced with 12 months of SDG 50 mg/day, a randomized, placebo-controlled clinical chemoprevention trial will be conducted wherein pre-menopausal women at increased risk for the development of breast cancer will receive Brevail® (200 mg, equivalent to 50 mg of SDG) or matched, blinded placebo for 12 months. A total of 242 subjects will be accrued, randomized 2:1 to SDG vs placebo, with the goal of achieving 220 subjects completing study and evaluable for biomarker change.

The primary objective is to determine if women randomized to 12 months of SDG exhibit greater change in the proportion of breast epithelial cells expressing the proliferation marker Ki-67/MIB-1 in hyperplastic benign breast tissue than do women randomized to placebo.

Secondary objectives are:

- 1) to determine if 12 months of SDG is associated with favorable modulation of other risk biomarkers including cytologic atypia, and serum levels of bioavailable estradiol and testosterone, IGF-I:IGFBP-3 ratio, c-peptide, adiponectin, and leptin.
- 2) to determine if Ki-67 and modulation of other risk biomarkers is correlated with change in blood or urine lignans.
- 3) to determine impact or potential impact on quality of life as measured by the BPQ breast pain questionnaire (a modified McGill Pain questionnaire), The Breast Cancer Prevention Trial (BCPT) Symptom Checklist a menstrual diary for cyclicity and cycle length for women not on cycle modulating contraceptives; and antimullerian hormone (AMH), a measure of follicular reserve.

An exploratory objective is to interrogate SDG's mechanism of action through measurement of changes in hormones, growth factors, gene expression, adipokines and cytokines and proteomic signatures.

The overriding hypothesis is that biomarkers assessed both in serum and in hyperplastic breast tissue obtained by RPFNA from high risk pre-menopausal women will be favorably modulated by 12 months of SDG without negatively affecting quality of life.

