5.10 Interruption or Discontinuation of Treatment

A genuine effort must be made to determine the reason(s) why a subject fails to return for the necessary visits or is discontinued from the trial. Information regarding the reason for not completing the trial will be recorded on the appropriate case report forms.

It will be documented whether or not each subject completed the clinical study. If for any subject study treatment or observations were discontinued the reason will be recorded on the appropriate case report form. Reasons that a subject may discontinue participation in a clinical study are considered to constitute one of the following:

- adverse event(s)
- abnormal laboratory value(s)
- abnormal test procedure result(s)
- subject develops breast cancer
- protocol violation
- subject withdrew consent
- lost to follow-up
- administrative problems
- physician decision
- death

All subjects that discontinue trial prematurely require notification of the Protocol Chair or her designee at KUMC within 72 hours of known discontinuation.

Any subject who receives at least one dose of study agent will be included in the safety analysis.

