Evaluation of agent-induced hormonal changes - We will examine whether SDG has any effects on serum levels of bioavailable estradiol, and testosterone, determined at baseline and after 12 months of study medication. We will determine whether addition of SDG alters the frequency or length of menstrual cycles. Effects on follicular reserve will be evaluated with anti-mullerian hormone in a sub-cohort of pre-menopausal women between ages 21 and 35 at study entry. Antimullerian hormone (AMH) is one of the earliest and most sensitive measures of follicular reserve declines for approximately 10 years before the cessation of menses. A distinct advantage for trial purposes is that it does not vary with day of menstrual cycle [119].

Adverse Events and Quality of Life – Change from baseline to 12 months will be assessed for mastalgia (expected in 30-50% of subjects at baseline), menstrual cycle and follicular reserve, and quality of life, as a function of SDG intake, plasma lignan levels and urinary lignan excretion. We will use the breast pain questionnaire (BPQ), which is a modified short form of the McGill Pain questionnaire (SF-MPQ) to assess breast discomfort and the Breast Cancer Prevention Trials (BCPT) Symptom Checklist to monitor quality of life

Correlative analyses will be performed with plasma and urine ENL and total lignans as the independent variable, with modifying variables of baseline BMI age and specific SNPs such as CYP17.

Since this is a phase IIB trial, the power and sample size for the primary endpoint was determined with a two-sided type I error rate of 5%. All subsequent secondary, tertiary and exploratory analyses will also be tested with a two-sided type I error rate of 5%. This may result in an elevated false positive rate for these secondary and tertiary analyses, however, since this is a Phase IIB study, we felt to control the type I error rate for the secondary, tertiary and exploratory analyses would be too conservative.

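### The toxicity comparison counts premature trial discontinuation as an event without limiting it to toxicity, so unrelated dropout enters the only specified between-arm test of adverse-event rates

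*Combined protocol and SAP*

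**What the plan says.** Section 11.2 introduces a comparison of moderate or worse toxicities and defines its event: "we will consider grade 3 toxicity or premature trial discontinuation as the critical events". It continues: "The prevalence of events in the SDG vs. the placebo arm will be examined by Fisher's exact test". On significance level, section 11.2 adds: "All subsequent secondary, tertiary and exploratory analyses will also be tested with a two-sided type I error rate of 5" per cent. No event rate, power or detectable difference is given for this test, and no other between-arm test of adverse-event rates is specified.

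Section 5.10 lists ten reasons for discontinuing. Besides adverse events and abnormal laboratory or test results, they include protocol violation, withdrawn consent, loss to follow-up, administrative problems and physician decision. On recording, it says: "If for any subject study treatment or observations were discontinued the reason will be recorded on the appropriate case report form".

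Three other places bear on the event:

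- Section 5.9, on agent-related grade 2 events that recur after the agent is resumed: "If toxicity again occurs, and is thought to be agent-related, the agent will be permanently stopped".
- Section 5.1 asks a woman who stops the agent early to attend for biomarker re-assessment as soon as she can.
- The safety set is stated twice. Section 5.10: "Any subject who receives at least one dose of study agent will be included in the safety analysis". Section 11.2: "All subjects randomized will be evaluable for safety".

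**The concern.** The event is meant to measure toxicity, but its second part carries no link to toxicity. Section 5.10 uses almost the same phrase for subjects who leave the trial early, directly after listing all ten reasons, so the protocol's own usage covers every cause. An analyst who follows section 11.2 literally would count a woman who moved away or was lost to follow-up as a critical toxicity event.

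Such dropout adds events that say nothing about SDG. Similar amounts in both arms raise both rates and the variance, and power falls. Unequal amounts can create or hide a difference. This matters because the background and impact sections (2.1 and 3.2) present SDG as an agent to be used without prescription or medical monitoring, and this test is the formal between-arm evidence on adverse events.

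There are two smaller ambiguities. It is not stated whether a woman whose agent is permanently stopped for recurrent grade 2 toxicity, but who attends early re-assessment, has discontinued the trial. And a woman who withdraws before her first capsule is an event under section 11.2 but outside the safety set under section 5.10.

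**Working it through.** **The plan's own figure.** The plan gives no power for the toxicity test. Its power for the primary endpoint reproduces. With 220 evaluable women split 2:1 (146.7 v 73.3), difference 2.5 and SD 6, the standard error is 6 × √(1/146.7 + 1/73.3) = 0.858. Then 2.5/0.858 − 1.96 = 0.95, which gives 83%. That figure does not bear on toxicity.

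**Inputs from the documents.**
- Arm sizes: "A total of 242 subjects will be accrued, randomized 2:1 to SDG vs placebo" (section 1.0), so 242 × 2/3 ≈ 161 SDG and 81 placebo.
- Test: Fisher's exact, two-sided, 5% (section 11.2).
- Planned dropout: 10% (section 3.0).
- Pilot: 45 of 49 completed and were evaluable, so 4/49 = 8.2% were not (section 2.4.4). There were two grade 3 events in 49 (4%). One was DCIS judged unrelated, and the other was pelvic pain judged possibly related, after which the subject discontinued (section 2.4.4.5).

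**Assumptions.** The documents give no toxicity rates by arm, so a range is shown. Unrelated dropout d is taken as independent of toxicity t. The composite rate in each arm is 1 − (1 − t)(1 − d). Power is exact, summing over all possible 161 v 81 tables.

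**Equal unrelated dropout of 8% in both arms.** Example: t = 10% gives 1 − 0.90 × 0.92 = 17.2%; t = 1% gives 1 − 0.99 × 0.92 = 8.9%.

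| Assumed toxicity, SDG v placebo | Composite rates at d = 8% | Power, toxicity events only | Power, composite |
|---|---|---|---|
| 12% v 2% | 19.0% v 9.8% | 80% | 43% |
| 10% v 1% | 17.2% v 8.9% | 82% | 38% |
| 8% v 2% | 15.4% v 9.8% | 41% | 19% |
| 6% v 2% | 13.5% v 9.8% | 19% | 10% |
| 4% v 1% | 11.7% v 8.9% | 9% | 7% |

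**Worked counts.** Toxicity events of 16/161 v 1/81 give p = 0.014. Adding 16 and 8 unrelated dropouts (about 10% of each arm) gives 32/161 v 9/81, p = 0.10.

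**Unequal unrelated dropout, equal true toxicity of 4%.**
- 8% SDG v 14% placebo: composite rates 11.7% v 17.4%. The test is significant about 21% of the time, with SDG looking safer.
- 14% SDG v 8% placebo: the rates reverse. The test is significant about 18% of the time, with SDG looking more toxic.
- Equal 10% in both arms: significant about 4% of the time.

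**The grade 2 question.** A woman whose agent is stopped for grade 3 toxicity is counted by the first part of the event in any case. The open group is therefore recurrent, related grade 2 stops. The pilot results give no frequency for these.

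**The case against.** *The context implies toxicity.* The sentence opens by naming toxicities, so a reader could take the discontinuation to be one caused by toxicity. That is a possible reading, but the text does not say it, and section 5.10 uses the near-identical phrase for all causes. It would be too strong to say that the sponsor intends to count every dropout; the documents leave the term undefined.

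*The large power losses depend on chosen rates.* This stands. SDG rates of 10% or more are well above the pilot's 4%, of which only one event in 49 (2%) was possibly related. At 4% v 1%, power is 9% without dilution. Redefining the event does not rescue a test that is weak at low rates.

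*The absolute excess barely shrinks.* This also stands. At 10% v 1% with 8% unrelated dropout, the difference moves from 9.0 to 17.2 − 8.9 = 8.3 points. Power and the ratio of rates fall, but a tabulated excess would still show.

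*The 8% is not a known unrelated rate.* Correct. If the pelvic-pain subject is among the four not evaluable, at most 3/49 (6%) were unrelated, and the documents do not give the others' reasons. At 6% dropout, power for 10% v 1% is 45% rather than 38%.

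*All-cause discontinuation is a recognised tolerability measure.* It is, and it needs no attribution of cause. That argues for keeping it as a separate comparison.

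*Stopping the agent is already recorded.* Section 8.2.2 has a field for the action taken on the agent, and section 5.9 provides a suspension page. These help the fix, but section 11.2 does not refer to them.

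**Conclusion.** The definition in section 11.2 should be tightened. As written, unrelated dropout enters the toxicity event; it costs power if balanced between arms and can bias the test in either direction if not. At 8% balanced dropout, the loss runs from 82% to 38% power at 10% v 1% down to 9% to 7% at 4% v 1%. These figures rest on assumed toxicity rates, independence of dropout and toxicity, and a dropout rate suggested by the planned 10% and the pilot's 8.2%.

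Two stronger inferences are not supported. The first is that the composite would hide an excess that a cleaner definition would reliably detect: near the pilot's grade 3 rate, neither definition has useful power. The second is that women stopped for toxicity are certain to be missed: grade 3 stops count anyway, and for recurrent grade 2 stops the documents do not settle the question. The mismatch in safety sets is real but small. Agent is dispensed at the study entry visit, where randomization takes place, so it concerns only women who withdraw before their first capsule.

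**What to change.** In section 11.2, define the discontinuation part of the event as permanent discontinuation of study agent because of an adverse event or abnormal laboratory value, whether or not the off-study procedures are done. Take it from the reason recorded under section 5.10 and the adverse-event field for action taken on the agent in section 8.2.2. Report all-cause discontinuation by arm and reason as a separate tolerability comparison. State one safety set and use it in both 5.10 and 11.2.

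The cost is analysis-plan wording, since the data items are already collected. There is a real downside: the restricted event depends on the recorded reason. A woman who leaves because of symptoms but is coded as withdrawn consent or lost to follow-up would drop out of it. The all-cause comparison kept alongside covers that gap.
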